A Phase II Study of Vaginal Testosterone Cream vs. the ESTRING for Vaginal Dryness or Decreased Libido in Early Breast Cancer Patients Treated with Aromatase Inhibitors

Protocol Number: CC# 067519
AZ Reference Number: IRUSANAS0071
IND Number: not applicable

Version Number: 9.0
Version Date: May 18, 2011

Study Drug: not applicable

Principal Investigator (Sponsor-Investigator)

[name].
UCSF Comprehensive Cancer Center
[name]
[name]
[contact]
[contact]

Co-Investigator
[name].

Statistician
[name]

Lead Clinical Research Coordinator

[name]
UCSF Comprehensive Cancer Center
[name]
[name]
[contact]

Clinical Research Coordinator
[name]
UCSF Comprehensive Cancer Center
[name]
[name]
[contact]
[contact]

Revision History		
Amendment #1	Version #1	30-JUL-2006
Amendment #2	Version #2	30-SEP-2006
Amendment #3	Version #2	10-DEC-2006
Amendment #4	Version #2	26-DEC-2006
Amendment #5	Version #3	21-FEB-2007
Amendment #6	Version #4	14-SEP-2007
Amendment #7	Version #4.1	13-NOV-2007
Amendment #8	Version #4.2	11-JAN-2008
Amendment #9	Version #5.0	05-MAR-2008
Amendment #10	Version #6.0	07-OCT-2008
Amendment #11	Version #7.0	22-DEC-2008
Amendment #12	Version #8.0	28-AUG-2009
		16-FEB-2010

PROTOCOL SYNOPSIS

A Phase II Study of Vaginal Testosterone Cream vs. the ESTRING for Vaginal Dryness or Decreased Libido in Early Breast Cancer Patients Treated with Aromatase Inhibitors

Principal Investigators

[name] and [name]

Study centre(s) and number of subjects planned

University of California, San Francisco 70 evaluable patients

Study period

10/1/07-3/31/10

Phase of development

Phase II

Objectives

Primary Objective

To evaluate the safety, based on serial measurements of serum estradiol levels, of intravaginal testosterone cream or the ESTRING administered for relief of vaginal dryness and/or decreased libido related to aromatase inhibitor therapy in early breast cancer patients.

Secondary Objectives

1. To document the systemic estradiol and testosterone levels at several time points in early breast cancer patients on aromatase inhibitors and being treated with intravaginal testosterone cream or the ESTRING.
2. To compare standard clinical laboratory measurements of serum estradiol with values of serum estradiol as measured by an ultrasensitive assay in a research laboratory.
3. To evaluate changes in gynecologic and sexual quality of life using validated questionnaires (the CARES Sexuality Subscales) in early stage breast cancer patients using intravaginal testosterone cream or the ESTRING for relief of vaginal dryness and/or decreased libido related to aromatase inhibitor therapy.

General design

Two-arm, randomized, open-label study.

Target subject population

Stage I-III breast cancer patients receiving aromatase inhibitors as adjuvant hormonal therapy and who have complaints of vaginal dryness, dyspareunia, or decreased libido. For this study, decreased libido is defined as a patient having decreased interest in sexual intercourse, decreased sexual arousal, or inability to achieve an orgasm.

Study treatments, dosage and mode of administration

- Testosterone Cream 1% micronized in velvachol - 0.5 gm of cream vaginally 3 times a week for total of 12 weeks of treatment
- ESTRING 2mg ring inserted vaginally once every 12 weeks

Duration of treatment

12 weeks

Safety

Patients will be monitored throughout the study for evidence of vaginal irritation, bleeding, or other side effects potentially related to the study treatments. Measurements of serum estradiol by standard clinical laboratory assays will be obtained at baseline, and at 4 and 12 weeks into treatment to assure that estradiol levels remain in the postmenopausal range. Throughout this protocol, a “persistently elevated estradiol level above the post-menopausal range” will be defined as the following:

1. An elevation of serum estradiol outside of the post-menopausal range of ≤ 10 pg/ml, and at least 10 pg/ml higher than the baseline value on two consecutive collections at least four weeks apart, and not including the baseline value which is drawn prior to the intervention is initiated.
2. If a patient’s baseline (day 1) serum estradiol level is > 10 pg/ml, the subsequent levels must be > 10 pg/ml higher than the baseline value to be considered a significant elevation outside the post-menopausal range.

Study Design

Up to 80 patients will be randomized to receive either testosterone or ESTRING so that 35 evaluable patients will receive each treatment. Randomization will attempt to balance the number of patients in each group based on self reported or medically documented depression, use of antidepressants, relationship status (single vs. partnered). Estradiol will be measured at baseline, at 4 weeks, and at 12 weeks into the study. If a patient is subsequently found to have a serum estradiol level outside of the post-menopausal range on day 1 of the study before the intervention begins (despite having a post-menopausal value during screening labs), this patient will be allowed to stay on study, and the subsequent estradiol level must be > 10 pg/ml higher than the baseline value to be considered a significant elevation outside the post-menopausal range. If a patient has an estradiol level outside of the post-menopausal range on the week 4 draw, or if there is a > 10 pg/ml increase in estradiol levels in patients with a baseline value above the post-menopausal range as described previously, they will have an additional lab draw at week 8.

Statistical methods

The primary outcome variable for determining safety at the end of the study is serial serum estradiol measurement. The test statistic is the number of patients that have a persistently elevated estradiol level above the post-menopausal range as described above. In the medical literature, there are no data to suggest what is “safe” or “unsafe” in terms of postmenopausal breast cancer patients being exposed to levels of estrogen above the postmenopausal range for a short duration of time (such as 12 weeks). No data exist to suggest that short term exposure to levels of estrogen above the post-menopausal range for up to 12 weeks would impact breast cancer recurrences. Therefore, it is fairly arbitrary to conclusively state that a certain rate of patients experiencing a short term increase in estradiol exposure with either of the treatment interventions (ESTRING or testosterone cream) is safe or unsafe. Taking this into consideration and after consulting with a number of breast cancer experts, we will consider each intervention “safe” if no more than 25% of patients in each arm have persistently elevated serum estradiol levels above the postmenopausal range after exposure to either of the study interventions.

The trial is designed to test the null hypothesis that a treatment is unsafe (25% or more of patients have a persistently elevated estradiol above the postmenopausal range) at a 5% level of significance. The alternate hypothesis is that a treatment is safe (i.e. fewer than 25% of patients have a persistently elevated estradiol above the postmenopausal range). Each treatment arm is tested separately. The trial is designed to have 98% power of concluding that a treatment is safe if the true failure rate is 5% and 70% power when the true failure rate is 10%.

Secondary Outcomes

A secondary outcome variable is the change in scores on the CARES Sexual Dysfunction Subscale from baseline to week 12. The ESTRING and testosterone cream treatment groups will be analyzed independently. A paired t-statistic will be used to compare week 12 to baseline values. With 35 patients in each treatment group (ESTRING and testosterone cream), we will have 90% power to detect an effect size of 0.41 based on a two-sided paired t-test at 5% level of significance.

Another secondary outcome variable will be the difference in the mean change in CARES Sexual Dysfunction Subscale from baseline to week 12 between the ESTRING and testosterone cream treatment groups. Using a two-sample t-test, and with 35 patients in each treatment group, we would have 90% power to detect a difference of 0.57 in the change scores (e.g. a reduction of 0.1 in one group vs. a reduction of 0.67 in the other group). Currently, there is no published research to suggest an expected effect size for these interventions. However, after carrying out this trial we will have estimates for the reduction for each treatment type and could use these estimates to plan a larger study to determine if one intervention is actually superior to the other.

TABLE OF CONTENTS

Section No.	Page No.
Protocol Title Page	1
Protocol Synopsis	3
Table of Contents	6
1.0 Introduction	8
1.1 Background	8
1.2 Rationale for this study	12
2.0 Study Objectives	13
2.1 Primary Objective	13
2.2 Secondary Objectives	13
3.0 Study Plan and Procedures	14
3.1 Overall study design	14

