7.3 Secondary Outcomes Statistical Analysis

A secondary outcome variable in this study is the change in the scores on the CARES Sexual Dysfunction Subscale from baseline to week 12 within each patient treatment group. The ESTRING and testosterone cream treatment groups will be analyzed independently. Another secondary outcome variable will be the difference in the change in CARES Sexual Dysfunction Subscale from baseline to week 12 between the ESTRING and testosterone cream treatment groups.

Based on results from previous studies investigating menopausal symptoms and sexual dysfunction in breast cancer survivors published by Ganz (11, 39), mean scores on the CARES Sexual Dysfunction Subscale (SDS) was 1.35 ± 1.13 for one group and 1.53 ± 1.17 for the other group (on a scale on 0-4). Within patient correlations were not published in either of these studies, but we would expect it to be 0.8 or greater. The formula for the sd when comparing 2 correlated measurements is: $\text{sd of difference} = \sqrt{2*\text{sd}^2*(1 - \text{cor})}$.

Based on a standard deviation of 1.17 from a study of different patients, a table for the $\text{sd}(\text{diff})$ as a function of the correlation is:

corr	$\text{sd}(\text{diff})$
0.7	0.91
0.8	0.74
0.9	0.52

With 35 evaluable patients in each treatment group (ESTRING and testosterone cream), we will have 90% power to detect an improvement of 0.41 when the correlation is 0.8, based on a two-sided paired t-test at 5% level of significance. This translates to a reduction from 1.53 to 1.12 for treated patients.

Using a two-sample t-test, and with 35 evaluable patients in each treatment group, we would have 80% power to detect a difference of 0.57 in the change scores (e.g. a reduction of 0.1 in one group vs. a reduction of 0.67 in the other group). Currently, there is no published research to suggest an expected effect size for these interventions. However, after carrying out this trial we will have estimates for the reduction for each treatment type and could use these estimates to plan a larger study to determine if one intervention is actually superior to the other.

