7.4 Analysis of serum estradiol and testosterone levels

Paired t-tests will be used to compare estradiol samples sent to the standard clinical laboratory utilized by UCSF (Quest Diagnostics) and those samples sent to a research lab in England that has reported the use of an ultrasensitive assay to detect very small changes in estradiol levels in postmenopausal women. With 35 samples we will have 90% power to detect a 0.564 sd difference between the two systems of measurements. We will also measure the correlation to assess the agreement between these two measurements. The data for one method will be plotted against the other method to determine whether the relationship between the two is linear over the range of values.

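### The same between-arm CARES comparison is given 90% power in the synopsis and 80% in section 7.3 (its inputs give about 89%), and the synopsis labels a 0.41-point change an effect size without its condition

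*Protocol*

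**What the plan says.** The synopsis (Secondary Outcomes) and section 7.3 both describe two analyses of the CARES Sexual Dysfunction Subscale from baseline to week 12.

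- **Between arms, two-sample t-test, 35 per arm.** Synopsis: "we would have 90% power to detect a difference of 0.57 in the change scores". Section 7.3: "we would have 80% power to detect a difference of 0.57 in the change scores". Both illustrate the difference with reductions of 0.1 and 0.67. Neither restates the significance level, the sidedness or the SD for this test.
- **Within arm, paired t-test.** Synopsis: "With 35 patients in each treatment group (ESTRING and testosterone cream") the claim is that "we will have 90% power to detect an effect size of 0.41 based on a two-sided paired t-test at 5% level of significance", with no SD and no correlation. Section 7.3: "90% power to detect an improvement of 0.41 when the correlation is 0.8, based on a two-sided paired t-test at 5% level of significance", followed by "This translates to a reduction from 1.53 to 1.12 for treated patients".

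Section 7.3 takes an SD of 1.17 for the score, tabulates the SD of change as 0.91, 0.74 and 0.52 at correlations 0.7, 0.8 and 0.9, and expects a correlation of at least 0.8. It notes that the correlation was not published in the studies it draws on.

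Section 7.4, for a different paired t-test (the two estradiol assays), says: "With 35 samples we will have 90% power to detect a 0.564 sd difference".

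Section 3.1 defines an evaluable patient by the baseline evaluation and the week-4 safety draw. Section 3.3.6 replaces only patients who do not start therapy or who miss that draw.

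**The concern.** A fixed difference, sample size, test and SD give one power. The two figures for 0.57 imply a chance of missing that difference of 10% in one place and 20% in the other, and a reader cannot tell which was meant. Both are in current text.

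The within-arm statement in the synopsis raises a second difficulty. In a power statement, effect size usually means a difference divided by its SD. On that reading the synopsis would need less than section 7.4 does for the same kind of test with the same 35 pairs: 0.41 SD against 0.564 SD, both at 90% power. A reader of the synopsis alone would take the trial to be more sensitive to small standardised changes than it is.

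At stake is how a null or borderline CARES result would be read. These are the only power statements for the efficacy comparisons.

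**Working it through.** **Inputs.** Score SD 1.17, correlation 0.8 and 35 per arm (section 7.3). Two-sided 5% is stated for the paired test and assumed for the two-sample test. Power is from the noncentral t distribution, with the normal approximation as a cross-check.

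**1. SD of change.** sqrt(2 × 1.17² × (1 − 0.8)) = sqrt(0.5476) = 0.740. This reproduces the tabulated 0.74; the 0.91 and 0.52 also reproduce.

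**2. Within-arm 0.41 in raw points.** 1.53 − 1.12 = 0.41, so section 7.3 is in scale points.
- Standardised: 0.41 / 0.74 = 0.554.
- Noncentrality: 0.554 × sqrt(35) = 3.28, df 34. Power 89.0% (normal approximation 90.6%).
- Working back by the normal approximation: (1.960 + 1.282) × 0.74 / sqrt(35) = 0.406, which rounds to 0.41.

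Section 7.3's 90% therefore reproduces. By exact t, 90% needs 0.564 × 0.74 = 0.417 points, a rounding difference only.

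**3. Within-arm 0.41 read as a standardised effect.**
- Noncentrality: 0.41 × sqrt(35) = 2.43, df 34. Power 65.4%.
- 90% power on this reading would need 65 pairs, or 0.564 SD with 35 pairs. The latter is exactly section 7.4's figure.

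**4. Between-arm 0.57.**
- Standardised: 0.57 / 0.74 = 0.770.
- Noncentrality: 0.770 × sqrt(35/2) = 3.22, df 68. Power 88.8% (normal approximation 89.7%).
- Working back by the normal approximation: 90% power gives (1.960 + 1.282) × 0.74 / sqrt(17.5) = 0.573, which rounds to 0.57; 80% power gives (1.960 + 0.842) × 0.74 / sqrt(17.5) = 0.496.
- Exact t: 90% power at 0.582, 80% power at 0.503.

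So 0.57 is the detectable difference for about 90% power, and about 0.50 is the one for 80%.

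**5. Does any stated input give 80% for 0.57?**

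| SD of change | Source | Power for 0.57, 35 per arm |
|---|---|---|
| 0.91 | correlation 0.7 | 73.3% |
| 0.74 | correlation 0.8 | 88.8% |
| 0.52 | correlation 0.9 | 99.5% |
| 0.715 | score SD 1.13, correlation 0.8 | 90.8% |

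A one-sided 5% test at SD 0.74 gives 93.9%. To obtain 80%, the SD of change would have to be about 0.84, that is a correlation of 1 − 0.839² / (2 × 1.17²) = 0.74. The protocol states neither value.

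**The case against.** The strongest reply is that nothing is miscalculated in the within-arm statement. Section 7.3 gives the units and the correlation, its 90% reproduces, and a synopsis may be brief. This stands. A reader might infer from the synopsis that the within-arm test really has 65% power rather than 90%. The documents do not support that: the 65% belongs to a 0.41 SD effect that section 7.3 shows was never the target. What remains is a wrong label and a missing condition.

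A second reply is that the 80% in section 7.3 errs on the cautious side, since it understates power at the assumed SD, and that its sentence restates no SD, so a correlation between the tabulated 0.7 and 0.8 might have been used. The direction is indeed harmless, but the synopsis still gives a different figure for an otherwise identical statement, and the only correlation section 7.3 adopts is 0.8.

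Two further inferences should be resisted.

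- **Planning of a later trial.** A reader might think the wrong powers would feed into it. The protocol says the observed reductions would be used for that, and these do not depend on the stated power.
- **Attrition.** A reader might conclude that week-12 losses seriously erode power. The protocol gives no dropout rate. Section 3.3.5 asks patients who stop early to attend a termination visit with the week-12 assessments, the section 3.2 schedule includes the questionnaires at early withdrawal, and section 3.1 allows them to be mailed or faxed. What stands is narrower: evaluability and replacement are tied to week 4, so those rules do not by themselves secure 35 week-12 scores per arm.

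**Conclusion.** The between-arm contradiction is real. At an SD of change of 0.74 and a two-sided 5% level (assumed for this test), power for a 0.57-point difference is about 89%. The synopsis figure of 90% fits within rounding, and section 7.3's 80% does not follow from its own inputs. The discrepancy is about 9 percentage points.

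The synopsis wording of the within-arm power is faulty in label only: 0.41 is raw points, equivalent to about 0.55 SD, with 89% power if the correlation is 0.8.

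Both conclusions rest on the score SD of 1.17, the unpublished correlation of 0.8, and 35 patients per arm with week-12 CARES scores. Severity is minor to moderate: the text is wrong as written, but it concerns secondary outcomes only. The sample size, the two-stage estradiol rule and the planned analyses are unaffected.

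**What to change.** 1. In both the synopsis and section 7.3, use one between-arm statement: *about 89% power for a difference of 0.57 points (80% for 0.50), assuming an SD of change of 0.74, correlation 0.8, two-sided 5% level*.
2. In the synopsis, replace the effect-size phrase with: *a mean change of 0.41 points (about 0.55 SD) if the correlation is 0.8*.
3. In both places, add that the figures assume 35 patients per arm with week-12 CARES scores, since evaluability requires only the baseline evaluation and the week-4 draw.

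If an SD other than 0.74 was intended for the between-arm test, state it and recompute the power from it.

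The cost is a wording amendment: no extra patients, visits or analyses.

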1. INTRODUCTION

1.1 Background

Aromatase Inhibitors in Breast Cancer

Approximately 211,300 new cases of breast cancer are diagnosed per year in the United States. Many breast cancer patients receive multi-modality therapy including surgery, chemotherapy and hormonal therapy. Hormonal therapy options for post menopausal women with early breast cancer include tamoxifen and aromatase inhibitors. Aromatase inhibitors are a class of compounds that act systematically to reduce the synthesis of estradiol from androgens in peripheral tissues. These compounds prevent estrogen biosynthesis by inhibiting the enzyme aromatase, which catalyses the conversion of adrenal androgens (androstenedione and testosterone) to estrogens (estrone and estradiol). Consequent reductions in estrogen levels have been shown to achieve objective responses in subjects with advanced breast cancer (1-3) and reductions in the risk of recurrence or disease progression in subjects with early breast cancer with hormone-receptor-positive disease (4).

Aromatase inhibitors have been shown to be an effective in reducing the risk of both local and distant recurrences in women with early breast cancer, and are approved as first line adjuvant hormonal therapy in post-menopausal women (5), as adjuvant hormonal therapy after 2-3 years of tamoxifen (6), and as extended adjuvant hormonal therapy in postmenopausal women who have completed five years of tamoxifen (7).

Sexual Dysfunction in Breast Cancer Patients

In the context of improved survival that has been observed in breast cancer patients over the last decade, it is important to address the long-term effects of breast cancer treatments on quality of life. There is a growing body of scientific literature to suggest that sexual functioning is one of the most distressing problems experienced by breast cancer survivors. One study of breast cancer patients who had surgery one year previously and had completed chemotherapy and radiation therapy found that 64% percent of the women experienced an absence of sexual desire, 38% had dyspareunia, and 42% lubrication problems (8). A study of 864 breast cancer survivors showed that scores on a 36 item general health survey were as good or better than those of healthy, age-matched women, and the frequency of depression was similar to general population samples. Marital/partner adjustment was similar to normal healthy samples, and sexual functioning mirrored that of healthy, age-matched postmenopausal women. However, sexual dysfunction occurred more frequently in women who had received chemotherapy, and in younger women who were no longer menstruating (9). In a much smaller study, the level of relationship distress among breast cancer survivors was the most significant variable affecting arousal, orgasm, lubrication, satisfaction, and sexual pain. This study also found that depression was an important determinant of lower sexual desire, and survivors on antidepressants had higher levels of arousal and orgasm dysfunction. Women who were older had significantly more concerns about vaginal lubrication and pain (10).

Estrogen Deprivation and Urogenital Atrophy in Breast Cancer Patients

Although many factors contribute to sexual dysfunction, a number of studies have shown that vaginal dryness is one of the most important predictors of sexual functioning for women with a history of breast cancer (11, 12). In the setting of estrogen deprivation, the mucosal and stromal tissues of the vagina, urethra, and trigone of the bladder undergo atrophy, resulting in decreased tissue elasticity and fluid secretion. This may lead to symptomatic vaginal dryness and irritation as well as dyspareunia. Estrogen deprivation also leads to an elevation in vaginal pH which may increase the risk of urinary tract infections.

While aromatase inhibitors are generally well tolerated, the incidence of vaginal dryness, dyspareunia, and loss of sexual interest in women taking this class of drugs is significant and particularly bothersome in women who have become post-menopausal rapidly due to systemic chemotherapy (13). These symptoms have a significant impact on quality of life and may lead to discontinuation of the drug in some patients. However, little has been published on the management of vaginal symptoms and sexual dysfunction related to hormonal therapy treatments for breast cancer.

Management of Urogenital Atrophy in Postmenopausal Women

Review of the literature on management of vaginal symptoms in post-menopausal women identifies several therapies that appear to be effective in improving or eliminating vaginal dryness and decreasing dyspareunia. Non-hormonal vaginal moisturizers have been shown to relieve urogenital symptoms, but are not as effective as vaginal estrogens in randomized trials (14). A multicenter, open-label, randomized, parallel-group study compared the efficacy and safety of 25-microgram 17beta-estradiol vaginal tablets (Vagifem) with 1.25-mg conjugated equine estrogen vaginal cream (Premarin Vaginal Cream) for the relief of atrophic vaginitis in 159 post-menopausal women (15). Both treatments provided equivalent relief of the symptoms of atrophic vaginitis based on composite scores of vaginal symptoms (dryness, soreness, and irritation). At weeks 2, 12, and 24, increases in serum estradiol concentrations and suppression of follicle-stimulating hormone were observed in significantly more patients who were using the vaginal cream than in those who were using the vaginal tablets ($p < 0.001$). Vaginal tablet therapy resulted in greater patient acceptance and lower withdrawal rates compared with vaginal cream therapy. In a double-blind placebo-controlled, 1612 post-menopausal patients with urogenital complaints were randomized to receive the Vagifem insert or placebo tablet once a day over a period of 2 weeks, and then twice a week for a total of the 12 months (16). The overall success rates of Vagifem vs. placebo on subjective and objective symptoms of vaginal atrophy were 85.5%, and 41.4%, respectively. A significant improvement of urinary atrophy symptoms was also seen in the Vagifem treated group as compared with the beginning of the study (51.9% vs. 15.5%, $P=0.001$). Therapy with the Vagifem insert did not raise serum estrogen level nor stimulated endometrial growth in this study.

An estradiol releasing vaginal ring (Estring) has been compared to a topical estriol cream (Synapause) in a 12 week treatment study in postmenopausal women. The Estring was found to be well tolerated, produced equivalent results in reducing vaginal symptoms, and was preferred by patients as less messy and easier to use (17). Clinical trials with Estring have shown that there is minimal systemic absorption of estradiol and the range of serum estradiol

levels measured at various time points fell within the post-menopausal range, making this an attractive option for women with a history of hormone receptor positive breast cancer (18).

A recent prospective randomized study compared the Estring to the Vagifem insert for relief of estrogen deficiency symptoms in post menopausal women over a period of 12 months (19). The primary endpoint was endometrial safety, based on the results of ultrasound measurement of endometrial thickness and a progestogen challenge test at baseline and week 48. Efficacy was determined by subjective assessment of urogenital estrogen deficiency symptoms and assessment of signs of vaginal epithelial atrophy by the clinician. There was no statistical difference between the groups in the alleviation of symptoms and signs of urogenital estrogen deficiency, and after 48 weeks of treatment, there was no statistically significant difference in endometrial thickness between the two groups. A statistically smaller proportion of bleeding/spotting occurred in the Estring group ($n = 0$) compared to the Vagifem users ($n = 4$). Estradiol and total estrone serum levels increased during treatment in both groups but remained within the normal postmenopausal range.

Safety of Vaginal Estrogen Preparations in Breast Cancer Patients

While the intravaginal estrogen preparations (creams, tablet inserts, and rings) are all reasonably effective in many post-menopausal patients, the level of systemic estrogen absorption is variable. One small study has raised concerns about a rapid rise in serum estradiol levels with the use of the Vagifem insert in post-menopausal breast cancer patients (20). Serum estradiol, follicle stimulating hormone (FSH) and luteinizing hormone (LH) levels were followed in seven postmenopausal women using the Vagifem insert while being treated with aromatase inhibitors for breast cancer. Serum estradiol levels, as measured by an assay specifically developed for measuring low levels in postmenopausal women, rose from baseline levels $</= 5$ pmol/l to a mean 72 pmol/l at 2 weeks into Vagifem treatment. By 4 weeks estradiol levels had decreased to <35 pmol/l in the majority (median 16 pmol/l) although two women continued to have further rises in estradiol levels. The authors concluded that Vagifem significantly raises systemic estradiol levels, at least early in the course of treatment for vaginal atrophy, and that in their opinion, this reversal of estradiol suppression is contraindicated in women being treated with aromatase inhibitors for breast cancer. It should be noted, however, that the impact of a very transient and unsustained rise in serum estradiol levels on the risk of recurrence in hormone receptor positive breast cancer is unknown. Furthermore, no studies have evaluated serum estradiol levels in post-menopausal breast cancer patients using the ESTRING for relief of urogenital symptoms. It is likely that due to its slow release mechanism, the levels of absorbed estrogens would be much lower than a rapidly dissolving tablet like the Vagifem insert.

Relationship Between Testosterone, Urogenital Symptoms and Sexual Function

In humans, the adrenal glands and the ovaries represent the main sources of circulating androgens in women. The adrenal steroid dehydroepiandrosterone (DHEA) represents the crucial precursor of human sex steroid biosynthesis. DHEA and its sulfate ester (DHEAS) are the most abundant steroids in the human circulation. DHEA, DHEAS and androstenedione do not have androgenic activity unless they are converted to testosterone and DHT, which can both bind and activate the androgen receptor. Testosterone can be converted either to dihydrotestosterone (DHT) or it can be aromatized towards estrogens. Therefore, an increase

in the circulating testosterone pool may be associated with increased estrogen generation within peripheral target tissues of sex steroid action. DHEA of adrenal origin may still be converted to testosterone within the postmenopausal ovary. A large cross-sectional study found no evidence of a significant decrease in circulating androgens during the menopause transition (21). While naturally occurring menopause does not appear to affect circulating androgen levels, oophorectomy and premature ovarian failure (such as that seen after chemotherapy for breast cancer), may lead to androgen deficiency (22, 23).

The issue of whether circulating androgen levels are associated with decreased sexual desire and arousability is hotly debated. A recently published cross-sectional study in a large cohort of Australian women ($n = 1423$) found no significant correlation of circulating androgen levels with self-reported perception of sexual desire and sexual satisfaction (24). Another large cohort study found that higher circulating testosterone levels were only minimally associated with increased sexual desire (25). The currently available data suggest that women with significant, near-total depletion of androgens (such as following a bilateral oophorectomy or with adrenal insufficiency) and concurrent complaints of impaired well-being and libido are the most likely to benefit from androgen replacement therapy (26). Beneficial effects on libido and mood have been reported in studies on testosterone replacement in surgically menopausal women (27-31). One of the most well conducted studies in this field evaluated 75 women who had undergone oophorectomy. Patients received conjugated equine estrogens (at least 0.625 mg per day orally) and then placebo, 150 micrograms of testosterone, and 300 micrograms of testosterone per day transdermally for 12 weeks each (32). The higher testosterone dose resulted in significant increases in scores for frequency of sexual activity and pleasure-orgasm compared to placebo. However, in almost all of these studies, androgens were administered concurrently with estrogen replacement, and in most patients, testosterone administration resulted in supraphysiological serum androgen concentrations. The impact of testosterone replacement in an estrogen depleted state has not been adequately addressed. Little is known about the effect of testosterone replacement in women with breast cancer, and nothing has been published documenting how effective it might be for relief of urogenital symptoms in women in an estrogen deprived state such as that created by aromatase inhibition.

Quality of Life Measurements in Breast Cancer Patients Receiving Adjuvant Therapy

As outcomes continue to improve in women with breast cancer, there has been an increasing interest in long term survivorship issues and the impact of adjuvant therapies on quality of life in breast cancer patients. A number of quality of life questionnaires have been tested and validated in breast cancer patients, including the FACT-B (Functional Assessment of Cancer-Breast) (33), and several have been developed that focus specifically on the endocrine, gynecologic, and sexual components of quality of life. These questionnaires include the FACT-ES (Functional Assessment of Cancer – Endocrine Subscale), and the CARES (Cancer Rehabilitation Evaluation System) Sexual Subscales. Using these questionnaires, and other survey tools, numerous studies have documented that adjuvant chemotherapy and hormonal therapies for breast cancer result in decreases in quality of life, particularly in relation to vasomotor symptoms and sexual functioning (8, 9, 11, 34, 35).

Side effects and quality of life issues associated with tamoxifen therapy have been well-described (36, 37). More recently, several large randomized trials of adjuvant hormonal

therapy have incorporated quality of life sub-studies, and the findings of these studies have been very informative in counselling patients on the significance of side effects, and in assisting in decision making about treatment and supportive care needs.

A quality of life subprotocol was conducted among 1,021 women participating in the Arimidex, Tamoxifen, Alone or in Combination (ATAC) Adjuvant Breast Cancer Trial during the first 2 years of treatment (13). Patients completed the Functional Assessment of Cancer Therapy-Breast (FACT-B) plus endocrine subscale (ES) at baseline and 3, 6, 12, 18, and 24 months, or until disease recurrence. Although endocrine symptoms increased between baseline and 3 months, overall quality of life improved for all groups during the 2-year period. Compared with patients receiving tamoxifen only, patients receiving anastrozole only reported more vaginal dryness, painful intercourse, and loss of sexual interest. A similar quality of life analysis was conducted among 582 patients in the Intergroup Exemestane Study (38). While quality of life was generally good and stable over 2 years, prevalence of severe endocrine symptoms at trial entry was high for vasomotor complaints and sexual problems, and these symptoms persisted for both the tamoxifen and exemestane treated patients throughout the study.

